8.4 Schedule of Visits, Measurements and Dosing

8.4.1 Scheduled Visits

Refer to Appendix 1 for a schedule of visits and measurements.

8.4.2 Unscheduled Visits

These visits may be performed in order to ensure subject safety. All procedures performed at an unscheduled visit will be recorded in the source documents and on the Unscheduled Visit eCRF pages. Any procedure indicated in the eCRF that is not performed should be indicated as “Not done.”

Evaluations that may be conducted at an Unscheduled Visit include:

- Slit-lamp Biomicroscopy;
- Visual Acuity;
- Intraocular Pressure;
- Pregnancy Test;
- Dilated Fundoscopy;
- Assessment of Adverse Events;
- Assessment of concomitant medications and/or treatments; and
- Any other assessments needed in the judgment of the investigator.

8.5 **Compliance with Protocol**

Subjects will be instructed on proper [REDACTED] instillation and storage of study drug at the end of Visits 1, 2, 3, and 4 and given written instructions.

[REDACTED]

[REDACTED] These guidelines will be used by the Investigator for determining the subject’s necessary compliance for the study and for recording deviations from this compliance.

8.6 **Subject Disposition**

8.6.1 Completed Subjects

A completed subject is one who has not been discontinued from the study.

8.6.2 Discontinued Subjects

Subjects may be discontinued prior to their completion of the study due to:

- adverse events;
- protocol violations;

- administrative reasons (e.g., inability to continue due to scheduling changes);
- lost to follow up;
- sponsor termination of study;
- subject choice (e.g. withdrawal of consent); and
- other

Note: In addition, any subject may be discontinued for any sound medical reason at the discretion of the investigator.

Notification of a subject discontinuation and the reason for discontinuation will be made to Ora and/or study sponsor and will be clearly documented on the eCRF.

8.7 Study Termination

The study may be stopped at any time by the investigator, the sponsor, and/or Ora with appropriate notification.

8.8 Study Duration

An individual subject's participation will involve 5 visits over approximately a 9-week period (63 days).

8.9 Monitoring and Quality Assurance

During the course of the study a monitor, or designee, will make routine site visits to review protocol compliance, assess study drug accountability and storage conditions, subject safety, and ensure the study is being conducted according to the pertinent regulatory requirements. The review of the subjects' medical records will be performed in a manner that adequately maintains subject confidentiality. Further details of the study monitoring will be outlined in a monitoring plan.

Regulatory authorities of domestic and foreign agencies, Ora, Inc. quality assurance, the sponsor and/or its designees may carry out on-site inspections and/or audits, which may include source data checks. Therefore direct access to the original source data will be required for inspections and/or audits. All inspections and audits will be carried out giving consideration to data protection as well as subject confidentiality to the extent that local, state, and federal laws apply.

9 ADVERSE EVENTS

9.1 Adverse Event

An adverse event is defined as any untoward medical occurrence associated with the use of a drug in humans, whether or not the event is considered IP-related. An adverse event can therefore be any unfavorable and unintended sign (e.g., an abnormal laboratory finding), symptom, or disease occurring after the subject started dosing with the IP,

without any judgment about causality. Any pre-existing medical condition that worsens after administration of the IP will also be considered a new adverse event.

If there is a worsening of a medical condition that was present prior to the administration of the IP, this should also be considered a new adverse event and reported. Any medical condition present prior to the administration of the IP that remains unchanged or improved should not be recorded as a treatment emergent adverse event at subsequent visits unless it worsens during treatment.

Investigational Product (IP) includes the investigational drug under evaluation and placebo, or any other medications required by the protocol given during any stage of the study.

Documentation regarding the adverse event should be made as to the nature, date of onset, end date, severity, relationship to IP, action(s) taken, seriousness, and outcome of any sign or symptom observed by the physician or reported by the patient upon indirect questioning.

9.1.1 Severity

Severity of an adverse event is defined as a qualitative assessment of the degree of intensity of an adverse event as determined by the investigator or reported to him/her by the patient/subject. The assessment of severity is made irrespective of relationship to IP or seriousness of the event and should be evaluated according to the following scale:

- *Mild*: Event is noticeable to the subject, but is easily tolerated and does not interfere with the subject's daily activities.
- *Moderate*: Event is bothersome, possibly requiring additional therapy, and may interfere with the subject's daily activities.
- *Severe*: Event is intolerable, necessitates additional therapy or alteration of therapy, and interferes with the subject's daily activities.

9.1.2 Relationship to Investigational Product

The relationship of each adverse event to the Investigational Product (IP) should be determined by the investigator using these explanations:

- *Definite*: When there are good reason and sufficient documentation to demonstrate a direct causal relationship between investigational product and AE;
 - *Probable*: When there are good reasons and sufficient documentation to assume a causal relationship in the sense of plausible, conceivable, likely but not necessarily highly probable.
 - *Possible*: When there is sufficient information to accept the possibility of a causal relationship in the sense of not impossible and not unlikely, although the connection is uncertain or doubtful, for example, due to missing data or insufficient evidence.
- None*: When there is sufficient information to accept a lack of a causal relationship, in the sense of impossible and improbable.

- *Unclassified*: When the causal relationship is not assessable for whatever reason due to insufficient evidence, conflicting data or poor documentation.

Suspected adverse reaction means any adverse event for which there is a reasonable possibility that the IP caused the adverse event. “Reasonable possibility” means there is evidence to suggest a causal relationship between the IP and the adverse event. Types of evidence that would suggest a causal relationship between the IP and the adverse event include: a single occurrence of an event that is uncommon and known to be strongly associated with drug exposure (e.g., angioedema, hepatic injury, Stevens-Johnson Syndrome); one or more occurrences of an event that is not commonly associated with drug exposure, but is otherwise uncommon in the population exposed to the drug (e.g., tendon rupture); an aggregate analysis of specific events observed in a clinical trial (such as known consequences of the underlying disease or condition under investigation or other events that commonly occur in the study population independent of drug therapy) that indicates those events occur more frequently in the drug treatment group than in a concurrent or historical control group.

9.1.3 Expectedness

The expectedness of an adverse event should be determined based upon existing safety information about the IP using these explanations:

- *Unexpected*: An adverse event that is not listed in the Investigator’s brochure or is not listed at the specificity or severity that has been observed.
- *Expected*: An adverse event that is listed in the Investigator’s brochure at the specificity and severity that has been observed.
- *Not Applicable*: Any adverse event that is unrelated to the IP.

Adverse events that are mentioned in the Investigator’s brochure as occurring with a class of drugs or as anticipated from the pharmacological properties of the drug, but are not specifically mentioned as occurring with the particular drug under investigation are to be considered unexpected.

The investigator should initially classify the expectedness of an adverse event, but the final classification is subject to the Medical Monitor’s determination.

9.2 **Serious Adverse Events**

An adverse event is considered serious if, in the view of either the investigator or sponsor, it results in any of the following outcomes:

- Death;
- A life-threatening adverse event;

Note: An adverse event is considered “life-threatening” if, in the view of either the investigator or sponsor, its occurrence places the patient or subject at immediate risk of death. It does not include an adverse event that, had it occurred in a more severe form, might have caused death.

- Inpatient hospitalization or prolongation of existing hospitalization;

Note: The term “inpatient hospitalization” refers to any inpatient admission (even if less than 24 hours). For chronic or long-term inpatients, inpatient admission includes transfer within the hospital to an acute/intensive care inpatient unit. Inpatient hospitalization does not include: emergency room visits; outpatient/same-day/ambulatory procedures; observation/short stay units; rehabilitation facilities; hospice facilities; nursing homes; or clinical research/phase 1 units.

Note: The term “prolongation of existing hospitalization” refers to any extension of an inpatient hospitalization beyond the stay anticipated or required for the reason for the initial admission as determined by the investigator or treating physician.

- A persistent or significant incapacity or substantial disruption of the ability to conduct normal life functions;

Note: A serious adverse event specifically related to visual threat would be interpreted as any potential impairment or damage to the subject’s eyes (e.g., hemorrhage, retinal detachment, central corneal ulcer or damage to the optic nerve).

- A congenital anomaly/birth defect.

Important medical events that may not result in death, are life-threatening, or require hospitalization may be considered serious when, based upon appropriate medical judgment, they may jeopardize the patient or subject and may require medical or surgical intervention to prevent one of the outcomes listed in this definition.

9.3 Procedures for Reporting Adverse Events

All adverse events and their outcomes must be reported to Ora, the study sponsor, and the IRB as required by the IRB, federal, state, or local regulations and governing health authorities and recorded on the appropriate eCRF.

9.3.1 Reporting a Suspected Unexpected Adverse Reaction

All adverse events that are ‘suspected’ and ‘unexpected’ are to be reported to Ora, the study sponsor and the IRB as required by the IRB, federal, state, or local regulations and governing health authorities.

If an investigator identifies a medical need for unmasking the treatment assignment of a subject, he/she should, if possible, contact Ora and/or the medical monitor prior to unmasking the identity of the IP. Ora will ask the site to complete and send them the Unmasking Request Form. Ora will notify Mitotech and jointly will determine if the unmasking request should be granted. They may consult the medical monitor as needed. The result of the request will be documented on the Unmasking Request Form. If approval is granted to unmask a subject, written permission via the Unmasking Request Form will be provided to the investigator. The investigator will unmask the subject using [REDACTED]. The investigator will complete the Unmasking Memo form and include it in the subject's study file and provide a copy for the Trial Master File (TMF). For each unmasked request, the reason, date, signature, and name of the person who unmasked the subject, must be noted in the subject's study file.

9.5 Type and Duration of the Follow-up of Subjects after Adverse Events

Adverse events that are ongoing at the end of the study visit will be followed. Phone calls will be placed with any subject who experiences an adverse event until the issue is resolved or the condition is considered ongoing and stable.

10 STATISTICAL HYPOTHESES AND METHODS OF ANALYSES

10.1 Analysis Populations

Intent-to-Treat Population – The intent-to-treat (ITT) population includes all randomized subjects. The primary and secondary efficacy analyses will be performed on the ITT population. Subjects in the ITT population will be analyzed as randomized.

Per-Protocol Population – The per protocol (PP) population excludes subjects with significant protocol deviations or who do not complete the study. Protocol deviations will be assessed and the per protocol population identified prior to database lock and unmasking. Subjects in the PP population will be analyzed as treated.

Safety Population – The safety population will include all subjects receiving treatment from whom at least one safety measurement is obtained following the first dose of study drug. The safety population will be analyzed for all safety assessments. Subjects in the Safety population will be analyzed as treated.

In addition, the following populations are defined for the primary and key secondary analyses of conjunctival fluorescein staining:

ITTCFS Population – The ITTCFS population includes all subjects in the ITT population with [REDACTED]

PPCFS Population – The PPCFS population includes all subjects in the PP population with [REDACTED]

The statistical analysis of safety data will be performed for the safety population. The primary efficacy analysis of Ocular Discomfort will be performed on the ITT population. The primary efficacy analysis of conjunctival fluorescein staining will be performed on

the ITTCFS population. Key secondary efficacy analyses will be performed on the ITT population, except for analysis of conjunctival fluorescein staining, which will be performed on the ITTCFS population. Exploratory efficacy analyses will be performed on the ITT population. The primary efficacy analysis procedures will also be performed on the PP and PPCFS populations as sensitivity analyses, for Ocular Discomfort and conjunctival fluorescein staining, respectively.

10.2 Statistical Hypotheses

The following statistical hypotheses will be tested, with H_{01} , H_{02} , H_{03} , H_{04} , H_{05} , H_{06} tested (in that order) comparing SkQ1 ophthalmic solution versus placebo. Each hypothesis test will be conditional upon the prior test(s) rejecting the null hypothesis. The statistical hypotheses are stated in terms of one-sided hypotheses, although statistical testing will be two-sided. Each test is therefore successful with respect to efficacy if the corresponding null hypothesis is rejected using a two-sided significance level of 0.05.

Primary Efficacy

H_{01} : There is no difference between SkQ1 ophthalmic solution and placebo for the change from baseline in Ocular Discomfort at Visit 5 (Day 57) [REDACTED]

H_{11} : The change from baseline in Ocular Discomfort at Visit 5 (Day 57) [REDACTED] is less with SkQ1 ophthalmic solution than with placebo.

H_{02} : There is no difference between SkQ1 ophthalmic solution and placebo for the change from baseline in conjunctival fluorescein staining (sum of temporal and nasal regions) at Visit 5 (Day 57) [REDACTED]

H_{12} : The change from baseline in conjunctival fluorescein staining (sum of temporal and nasal regions) at Visit 5 (Day 57) [REDACTED] is less with SkQ1 ophthalmic solution than with placebo [REDACTED]

Key Secondary Efficacy

H_{03} : There is no difference between SkQ1 ophthalmic solution and placebo for the change from baseline in Ocular Discomfort at Visit 3 (Day 29) [REDACTED]

H_{13} : The change from baseline in Ocular Discomfort at Visit 3 (Day 29), [REDACTED] is less with SkQ1 ophthalmic solution than with placebo.

H_{04} : There is no difference between SkQ1 ophthalmic solution and placebo for the change from baseline in conjunctival fluorescein staining (sum of temporal and nasal regions) at Visit 4 (Day 43), [REDACTED]

H₁₄: The change from baseline in conjunctival fluorescein staining (sum of temporal and nasal regions) at Visit 4 (Day 43), [REDACTED] is less with SkQ1 ophthalmic solution than with placebo [REDACTED]

H₀₅: There is no difference between SkQ1 ophthalmic solution and placebo for the pre- to post-CAE[®] change in tear film break-up time at Visit 5 (Day 57) in the worst eye.

H₁₅: The pre- to post-CAE[®] change in tear film break-up time at Visit 5 (Day 57) in the worst eye is greater with SkQ1 ophthalmic solution than with placebo.

H₀₆: There is no difference between SkQ1 ophthalmic solution and placebo for the change from baseline in corneal fluorescein staining in the central region at Visit 3 (Day 29). [REDACTED]

H₁₆: The change from baseline in corneal fluorescein staining in the central region at Visit 3 (Day 29). [REDACTED] is less with SkQ1 ophthalmic solution than with placebo.

10.3 Sample Size

To address the multiple primary efficacy variables employed in this study, the sample size calculations have been based on a hierarchical structure. In order to test a variable, the preceding variable(s) must have shown statistically significant improvements versus placebo using a two-sided significance level of 0.05. Using these strategies, the Type I error rate will be maintained at the 0.05 significance level for the primary efficacy variables.

[REDACTED]

[REDACTED]

[REDACTED]

[REDACTED] enrollment of 284 patients per group would be required for 90% power for each endpoint to detect the differences between the active treatment group and placebo group.

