the preceding variable(s) must have shown statistically significant improvements versus placebo using a two-sided significance level of 0.05. Using these strategies, the Type I error rate will be maintained at the 0.05 significance level for the primary efficacy variables.

This study is expected to enroll 300 subjects in the active treatment arm and 300 subjects in the placebo group [REDACTED]

[REDACTED]

[REDACTED] enrollment of 284 patients per group would be required for 90% power for each endpoint to detect the differences between the active treatment group and placebo group.

Primary Efficacy Analyses

Efficacy analyses will be performed on the ITT and ITTCFS populations, for Ocular Discomfort and conjunctival fluorescein staining endpoints, respectively. Supportive analyses will be performed on the PP and PPCFS populations, for Ocular Discomfort and conjunctival fluorescein staining endpoints, respectively.

Primary efficacy endpoints are:

- Change from baseline (Visit 2) in Ocular Discomfort in the worst eye at Visit 5 (Day 57) [REDACTED]
- Change from baseline (Visit 2) in conjunctival fluorescein staining (sum of temporal and nasal regions) in the worst eye at Visit 5 (Day 57) [REDACTED]

The primary efficacy endpoint of conjunctival fluorescein staining (sum of temporal and nasal regions) will be tested in the pre-specified subgroup [REDACTED]

The primary efficacy endpoints will be analyzed using an analysis of covariance (ANCOVA) model [REDACTED]

[REDACTED] The adjusted least squares means and their

standard errors (SEs) will be presented along with their two-sided 95% confidence intervals (CIs) for each treatment group and the difference between the active treatment group and the placebo treatment group. In addition, a two-sample t-test will be used to compare the active and placebo groups in the change from baseline at Visit 5 [REDACTED]. The mean difference, SD for the difference, and the 95% CI for the difference will be presented. A two-sided p-value < 0.05 will be considered statistically significant.

The primary analyses for both primary endpoints will be conducted on the ITT and ITTCFS populations for Ocular Discomfort and conjunctival fluorescein staining, respectively, using the Markov Chain Monte Carlo (MCMC) multiple imputation method to impute missing data. [REDACTED]

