3 CLINICAL HYPOTHESES

The clinical hypotheses for this study is that SkQ1 ophthalmic solution 1.55µg/mL is superior to placebo for the primary endpoints of signs and symptoms, as follows:

- Subjects receiving SkQ1 ophthalmic solution will have a statistically significantly lower mean change from baseline (Visit 2) in Ocular Discomfort at Visit 5 (Day 57) [REDACTED]
- Subjects receiving SkQ1 ophthalmic solution will have a statistically significantly lower mean change from baseline (Visit 2) in conjunctival fluorescein staining (sum of temporal and nasal regions) at Visit 5 (Day 57) [REDACTED]

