6.1.3 Criteria for Effectiveness

The primary efficacy variables will be evaluated to assess effectiveness. For this phase 3 study, the primary analyses will each be evaluated at two-sided alpha levels of 0.05 (SkQ1 ophthalmic solution versus placebo) to determine evidence of efficacy. Testing will follow a hierarchical testing strategy, where efficacy for each endpoint and comparison to placebo will be determined only if the preceding test(s) are statistically significant.

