10.4.4 Multiplicity Adjustments

The primary and key secondary efficacy analyses will be tested following a hierarchical testing strategy in order to maintain a study-wide type I error rate of 0.05 while testing the primary and key secondary hypotheses. The testing strategy will proceed as follows:

- 1) Compare the change from baseline in Ocular Discomfort at Visit 5 (Day 57) [REDACTED] between SkQ1 and placebo. If statistically significant at a two-sided $\alpha = 0.05$, proceed to step 2; otherwise no further testing will be performed and all other testing is considered exploratory.
- 2) Compare the change from baseline in conjunctival fluorescein staining (sum of temporal and nasal regions) at Visit 5 (Day 57) [REDACTED] in the worst eye between SkQ1 and placebo. [REDACTED] If statistically significant at a two-sided $\alpha = 0.05$, proceed to step 3; otherwise no further testing will be performed and all other testing is considered exploratory. Compare the change from baseline in Ocular Discomfort at Visit 3 (Day 29) [REDACTED] between SkQ1 and placebo. If statistically significant at a two-sided $\alpha = 0.05$, proceed to step 4; otherwise no further testing will be performed and all other testing is considered exploratory.
- 3) Compare the change from baseline in conjunctival fluorescein staining (sum of temporal and nasal regions) at Visit 4 (Day 43), [REDACTED] between SkQ1 and placebo. [REDACTED] If statistically significant at a two-sided $\alpha = 0.05$, proceed to step 5; otherwise no further testing will be performed and all other testing is considered exploratory.

- 4) Compare the tear film break-up time pre- to post-CAE[®] change at Visit 5 (Day 57) in the worst eye between SkQ1 and placebo. If statistically significant at a two-sided alpha = 0.05, proceed to step 6; otherwise no further testing will be performed and all other testing is considered exploratory.
- 5) Compare the change from baseline in corneal fluorescein staining in the central region at Visit 3 (Day 29) [REDACTED] [REDACTED] between SkQ1 and placebo. All other testing is considered exploratory.

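### Does 90% power for each endpoint overstate the chance of declaring the second primary endpoint in the fixed sequence?

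*Combined protocol and SAP*

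**What the plan says.** Protocol section 10.3 says that "the sample size calculations have been based on a hierarchical structure". It explains that a variable is tested only once those ahead of it are significant at two-sided 0.05, and that this keeps the type I error at 0.05 for the primaries. Several blacked-out lines follow. The text resumes partway through a sentence: "enrollment of 284 patients per group would be required for 90% power for each endpoint to detect the differences". The synopsis gives the same figure and adds the planned enrolment: "This study is expected to enroll 300 subjects in the active treatment arm and 300 subjects in the placebo group".

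Three other sections fix the order of testing:

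- Section 10.2: "Each hypothesis test will be conditional upon the prior test(s) rejecting the null hypothesis".
- Section 10.4.4, after the Ocular Discomfort comparison: "proceed to step 2; otherwise no further testing will be performed and all other testing is considered exploratory".
- Section 6.1.3: efficacy on each endpoint "will be determined only if the preceding test(s) are statistically significant".

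Section 3 states the clinical hypothesis that the active solution "is superior to placebo for the primary endpoints of signs and symptoms, as follows", and then lists Ocular Discomfort and conjunctival staining separately. Section 10.1 places the Ocular Discomfort analysis in the ITT population and the staining analysis in ITTCFS, a subset of ITT whose definition is blacked out.

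**The concern.** A power quoted for each endpoint normally means the power of each test taken alone. Under a fixed sequence that figure holds for the first test only. Staining needs two rejections, its own and the one before it, so its chance of being declared cannot exceed the smaller of the two stand-alone powers. It falls below that unless a rejection on the endpoint with the smaller power is always accompanied by one on the other.

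The section says the calculation rests on the hierarchy. A reader could therefore take 90% as the chance of declaring the sign endpoint, or of supporting both the sign and the symptom hypotheses in section 3. If each test has exactly 90% alone at 284 per group, the risk of missing staining is about 17% to 19%, not 10%. A sponsor who wanted 90% for both would need a larger trial than the one described.

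**Working it through.** **Inputs from the documents.** Two-sided alpha 0.05 per test (section 10.2); 1:1 allocation (section 5.1); 284 per group for 90% per endpoint (section 10.3); 300 per group planned (synopsis); fixed sequence (sections 6.1.3, 10.2, 10.4.4).

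**Inputs that are not legible.** Effect sizes, standard deviations, dropout, the size of ITTCFS, and the correlation between the two tests. The stand-alone powers and correlations below are therefore assumptions.

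**Step 1: the plan's own figure.** Without effect sizes, 284 cannot be reproduced independently. Solving backwards for the standardised difference with the normal formula:

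d = (z₀.₉₇₅ + z₀.₉₀) × √(2/284) = (1.960 + 1.282) × 0.0839 = 0.272

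The noncentral t gives 0.2725. This is circular. It shows only that 284 is a possible single-endpoint answer.

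**Step 2: stand-alone power at the planned 300.** If all 300 contribute and the effect is the same:

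Φ(0.272 × √(300/2) − 1.960) = Φ(1.37) = 91.5%

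An endpoint with 95% at 284 (d = 0.303) has 96.0% at 300. One with 99% at 284 (d = 0.360) has 99.3% at 300.

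**Step 3: power through the sequence.** With stand-alone powers p₁ and p₂, and correlation ρ between the test statistics:

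P(staining declared) = P(both reject) = Φ₂(z(p₁), z(p₂); ρ)

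At ρ = 0 this is the product p₁ × p₂; for example, 0.90 × 0.90 = 0.810.

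| Stand-alone powers | Per group | ρ = 0 | ρ = 0.3 | ρ = 0.5 |
|---|---|---|---|---|
| 90% and 90% | 284 | 81.0% | 82.2% | 83.2% |
| 91.5% and 91.5% | 300 | 83.7% | 84.7% | 85.6% |
| 90% and 95% | 284 | 85.5% | 86.2% | 86.9% |
| 91.5% and 96.0% | 300 | 87.8% | 88.4% | 88.9% |
| 90% and 99% | 284 | 89.1% | 89.3% | 89.5% |
| 91.5% and 99.3% | 300 | 90.8% | 91.0% | 91.1% |

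For 90% and 90% at 284, a correlation of 0.9 gives 86.9%. With no assumption about correlation, the limits are 0.90 + 0.90 − 1 = 80% and 90%.

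**Step 4: the subset.** Analysing staining in a fraction f of the ITT population scales the correlation of the test statistics by about √f. With f = 0.5, a correlation of 0.5 becomes 0.354, and the 90%/90% case gives 82.4% instead of 83.2%. That moves the result towards the lower end of its range but changes little.

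**Step 5: what 90% on both would need.** With equal effects of the size in step 1, about 349, 344 or 339 per group at ρ = 0, 0.3 or 0.5.

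**Step 6: is anything stated wrongly?** The legible text attaches 90% to each endpoint. It does not attach it to the pair or to the sequence. The first primary keeps its full stand-alone power, and type I error control is unaffected.

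**The case for a change.** The best case for acting is that the logic needs no hidden input. The protocol's own rules make the power for staining equal to the power for both, and that cannot exceed the smaller stand-alone figure. A trial with two primaries in sequence serves its readers better if it states the power for the second, and doing so costs one sentence. Staining is also analysed in a subset. If that subset falls below 284 per group and the calculation did not allow for it, its power is lower again.

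The probability argument stands in full. What does not stand is the step from there to a defect in the plan. The words just before the 284 figure are blacked out, and that is where the effect sizes, the allowance for the subset and any sequential power would be given. Text hidden by redaction cannot be counted as absent. The section also says that the calculation considered the hierarchy, and it describes the testing condition before giving the power, so an attentive reader is warned.

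The 81% to 83% figure also needs two endpoints, on different scales and in different populations, to have exactly the same power at one sample size. It is more natural to suppose that 284 is set by the more demanding endpoint and that the other has some margin. The last row of the table shows the shortfall disappearing when that margin is large and all 300 per group contribute.

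**Conclusion.** No change to the plan follows. The 90% is stated per endpoint, and read that way it is not shown to be wrong. The power to declare staining through the sequence is lower than its stand-alone power by an amount that the public text cannot settle. It is 81% to 83% if both tests have exactly 90% at 284 per group and their correlation is 0 to 0.5. It runs from about 81% to 91% when one endpoint may have up to 99% and the number per group is 284 to 300. These ranges rest on assumed stand-alone powers and correlations, and on effects solved backwards from 284.

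A fuller description would not alter enrolment, alpha, the order of testing, the analysis or the reading of the results. If the unredacted section does not already give the sequential power, the sponsor can compute it from its own inputs and report it as a descriptive figure. That would be a clarification of the text, not the correction of an error.
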